## **1.6 First results VOICE trial**

Between February 17th and March 12th, 2021, 791 participants were enrolled in the current trial. For the primary endpoint at 28 days after the second vaccination, 743 participants were evaluable (per-protocol population): 240 individuals without cancer and 131 patients receiving immunotherapy, 229 patients receiving chemotherapy, and 143 patients receiving chemo-immunotherapy. SARS-CoV-2-binding antibody response (>10 binding antibody units (BAU)/mL) was found in 100%, 99.3%, 97.4%, and 100% of the participants in cohorts A, B, C, and D, respectively.

Given the importance for clinical decisions, we defined, based on neutralizing capacity, a cutoff level at 300 BAU/mL to discriminate between suboptimal and adequate responders. Twenty eight days after the second vaccination, 99.6% (A), 93.1% (B), 83.8% (C), and 88.8% (D) had an adequate response. Spike-specific T cell responses were detected in almost half of the suboptimal and non-responders. No new safety signals were observed [36].

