#### 1.7 Third vaccination

Although most patients with solid tumors develop an adequate SARS-CoV-2-binding antibody response after vaccination, 6.9%, 16.2%, and 11.2% of patients treated with immunotherapy, chemotherapy, and chemo-immunotherapy, respectively, are still suboptimal or non-responders. As most of them show an increase in antibody concentration after the second vaccination, an additional third vaccination might turn them into adequate responders. In the extension of the VOICE trial, we will investigate whether non and suboptimal responders might benefit from a third vaccination. We will study whether an additional mRNA-1273 administration can improve the antibody response of participants in the VOICE trial who had a low antibody response on day 28 following two mRNA-1273 vaccinations. In addition safety, neutralizing antibodies and SARS-CoV-2 Spike-specific interferon-gamma T cell response will be studied.

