			28	180	Vacc3 ad	28	Day	540
			Vacc2			vacc3	330	
SARS-Cov-2	х	х	х	х	х	х	х	х
antibodies								
PBMC isolation	х		х	х	х	х	х	х
for in depth								
cellular								
immune								
response								
Routine	х	х	х	х	х	х	х	х
hematology b								
Routine	х	х	х		х	х		
chemistry c								

Table 2: Blood tests

PBMC = peripheral blood mononuclear cells

a Blood has to be drawn before vaccination

b Hemoglobin, red blood cell count, platelet count, white blood cell count, white blood cell differential

c glucose, creatinine, aspartate aminotransferase (ASAT), alanine aminotransferase (ALAT), albumin, lactate dehydrogenase (LDH), C-reactive protein (CRP).

d Only participants with an inadequate antibody response (≤300BAU/mL) on day 28 after the second vaccination.

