SARS-CoV-2 specific T cell response will be measured at baseline, and at 28 days after the second and third vaccination, and 6, 11 and 18 months after the second vaccination and expressed as the number of IFN-γ producing SARS-CoV2 specific T cells/million PBMC. To assess the contribution of CD8+ T cells in this response, we will assess the number of IFN-γ producing T cells after blocking with an MHC class I antibody. This will be expressed as the number of IFN-γ producing CD4+ T cells/ million PBMCs. Subtraction of the number of responding CD4+ T cells from the total number of responding T cells will lead to the number of IFN-γ producing CD8+ T cells/ million PBMCs. Results will be compared between each patient cohort and the cohort of individuals without cancer using ANOVA or Kruskal–Wallis one-way analysis of variance, and Welch t-tests or Mann-Whitney U tests, depending on the distribution of the data.

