#### 10.3 Other study parameters

- Dynamics of SARS-CoV-2 specific antibody concentrations will be analyzed, e.g. by calculating geometric mean fold-rise between baseline and post-baseline time points and antibody decay after day 28.
- In-depth flow-cytometric analyses for functional and phenotypical characterization of SARS-CoV-2 specific cellular responses will be performed by assigning proliferative capacity, cytokine production and phenotypical markers (>25 markers in parallel) in a subset of patients. These descriptive study parameters will not be statistically compared between cohorts.
- Baseline (immune) parameters will be related to vaccination response using univariate analysis.
- As a functional readout, the neutralizing capacity SARS-CoV-2 antibodies will be measured at baseline, 28 days and 6, 11 and 18 months after the second vaccination. Titers will be expressed as GMCs with 95% CIs for each cohort, for each time point.
- To assess induction of a mucosal antibody response, mucosal lining fluid samples will be collected for measurement of SARS-CoV-2-specific antibody concentrations with multiplex immunoassay at baseline and at 28 days after the second vaccination. Additional analyses e.g. neutralizing capacity of mucosal antibodies can be performed.
- Mucosal SARS-CoV-2-specific antibody response will be correlated with serum SARS-CoV-2-specific antibody response.

- Information on incidence of SARS-CoV-2 infection, outcome of COVID-19 during 18 months after the second vaccination will be collected. The number of participants tested, the number of SARS-CoV-2 tests and test results will be reported. For participants with a positive test, information about severity will be presented including hospital admissions, use of oxygen, intensive care admission and mechanical ventilation.
- Levels of SARS-CoV-2 S-specific IgG antibodies before the third vaccination, and at day 28 after the third vaccination will be measured to assess antibody response in participants with an inadequate response to two mRNA-1273 vaccinations.
- Safety of a third mRNA-1273 vaccination in participants with an inadequate response to two mRNA-1273 vaccinations as mentioned under 10.2.

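### The third-dose T cell analysis in 10.2 has almost no same-visit comparator and no within-person contrast, and 10.3 schedules no neutralisation at day 28 after dose 3

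*Combined protocol and SAP*

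**What the plan says.** **T cells.** Section 10.2 states: "SARS-CoV-2 specific T cell response will be measured at baseline, and at 28 days after the second and third vaccination", with further visits at 6, 11 and 18 months after dose 2. One comparison sentence covers all of these visits: "Results will be compared between each patient cohort and the cohort of individuals without cancer using ANOVA" or Kruskal–Wallis, followed by Welch t or Mann-Whitney tests. Section 8.1.3 also lists the T cell response 28 days after dose 3 as exploratory, without a comparator.

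**Who gets dose 3 in the study.** Footnotes to Tables 1 and 2 restrict it to participants at or below 300 BAU/mL on day 28 after dose 2. Section 1.6 reports: "Twenty eight days after the second vaccination, 99.6% (A), 93.1% (B), 83.8% (C), and 88.8% (D) had an adequate response".

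**Samples.** Table 2 marks "PBMC isolation" at Vacc 3, and its footnote requires the draw to precede the injection. Antibody blood is also drawn at Vacc 3 and 28 days later.

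**Neutralisation.** Section 1.7 says of the extension: "In addition safety, neutralizing antibodies and SARS-CoV-2 Spike-specific interferon-gamma T cell response will be studied". Section 10.3 gives the schedule: "the neutralizing capacity SARS-CoV-2 antibodies will be measured at baseline, 28 days and 6, 11 and 18 months after the second vaccination". The same section does plan binding IgG before dose 3 and 28 days after it.

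**The concern.** The extension asks whether a further dose improves immunity in people who responded poorly to two. The contrast that answers this is before versus after dose 3 in the same person. For T cells the plan states no such contrast. It applies a between-cohort comparison whose control side, at that visit, is nearly empty because almost every control was an adequate responder.

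For neutralisation, no post-dose-3 measurement is tied to the dose. This matters because section 1.6 says the 300 BAU/mL cutoff, which decides who is offered dose 3, was based on neutralising capacity. The 11-month visit is a poor substitute: section 1.8 expects most participants to have had extra vaccinations by January 2022.

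**Working it through.** **Inputs.** Section 1.6 gives the evaluable numbers: "743 participants were evaluable (per-protocol population): 240 individuals without cancer and 131 patients receiving immunotherapy", "229 patients receiving chemotherapy, and 143 patients receiving chemo-immunotherapy". It also gives the adequate-response rates quoted above. Section 1.7 gives the inadequate shares among patients as 6.9%, 16.2% and 11.2%. The plan sets no alpha for the T cell tests, so two-sided 0.05 is an assumption here.

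**Step 1: reproduce the plan's figures.** For each cohort I looked for whole-number counts that round to the stated rate. Only one count fits in each.

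| Cohort | Adequate | Stated | Inadequate |
|---|---|---|---|
| A | 239/240 = 99.58% | 99.6% | 1 (0.4%) |
| B | 122/131 = 93.13% | 93.1% | 9 (6.9%) |
| C | 192/229 = 83.84% | 83.8% | 37 (16.2%) |
| D | 127/143 = 88.81% | 88.8% | 16 (11.2%) |

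For cohort A, 238/240 would be 99.2%, so two controls do not fit. The patient shares match section 1.7. In all, 1 + 9 + 37 + 16 = 63 evaluable participants qualify, 62 of them patients.

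**Step 2: the planned tests with one control and full uptake.** Welch's t needs a variance in each group, and one value gives none. For Mann-Whitney with one control and m patients, the control's rank has m + 1 equally likely positions, so the smallest exact two-sided p is 2/(m + 1):

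- B: 2/10 = 0.20
- C: 2/38 = 0.053
- D: 2/17 = 0.118

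ANOVA or Kruskal–Wallis can be run, but cohort A adds no information on variance. A pooled-variance t contrast of one control against each cohort needs a difference of about 3.4 (B), 2.9 (C) or 3.1 (D) SD for 80% power.

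**Step 3: if one more control qualified.** Of 791 enrolled, 791 − 743 = 48 were not evaluable, and the split by cohort is not given. With two controls the floor is 2 divided by the number of ways to choose 2 from m + 2: 2/55 = 0.036 (B), 2/741 = 0.003 (C), 2/153 = 0.013 (D). Power stays poor. In the best case, cohort C, the standard error is SD × √(1/2 + 1/37) = 0.73 SD. Multiplying by 1.96 + 0.84 = 2.80 gives a detectable difference of about 2.0 SD.

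**Step 4: the within-person alternative.** The smallest standardised change detectable with 80% power at two-sided 0.05 is roughly 2.80/√n, or slightly more with the noncentral t. Uptake of dose 3 is not given, so a range is shown for the pooled estimate.

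| Uptake | Pooled B–D n | 2.80/√n | Noncentral t |
|---|---|---|---|
| 100% | 62 | 0.36 | 0.36 |
| 75% | 46 | 0.41 | 0.42 |
| 50% | 31 | 0.50 | 0.52 |

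By cohort at full uptake, the noncentral t gives about 1.07 (B, n = 9), 0.47 (C, n = 37) and 0.75 (D, n = 16).

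**Step 5: visits around dose 3, side by side.**

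| Measure | Pre-dose Vacc 3 | Day 28 after Vacc 3 |
|---|---|---|
| Blood drawn (Table 2) | PBMC and antibody | PBMC and antibody |
| Binding IgG (10.3) | named | named |
| T cell ELISpot (8.1.2, 10.2) | not named | named |
| Neutralisation (10.3) | not named | not named |

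**The case against.** A reader might infer that the extension cannot answer its T cell and neutralisation questions at all. The documents do not support that, for five reasons.

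- **The comparator is not spelled out.** Section 10.2 names cohort A, not controls who had a third dose. Patients after three doses could be set against about 240 controls after two. That reading is open, but it compares patients selected for a low antibody response with unselected controls at a different dose number and time. It works as a benchmark, not as a test of what dose 3 did.
- **Section 10 has safeguards.** It requires test assumptions to be checked, provides for descriptive statistics, and promises individual data for primary and secondary parameters. A meaningless p-value is therefore not inevitable. None of this states a paired analysis.
- **The 6-month sample may fall shortly before dose 3.** In Table 1 Vacc 3 follows day 180. Enrolment ran from 17 February to 12 March 2021. If the first dose was given at enrolment and the second 28 days later (both assumptions), day 180 falls between about 13 September and 6 October 2021. T cells and neutralisation are both planned then, so it would be wrong to say that nothing is measured before dose 3. The visit is not tied to the dose, however, and the interval is not stated.
- **The Vacc 3 PBMCs are not necessarily unused.** The flow cytometry in 10.3 names no visits and could draw on them in a subset.
- **The neutralisation promise stands in the introduction.** The formal third-dose objectives in section 2 are binding antibody concentration and safety, and 8.1.3 lists neutralisation without visits. Even so, 1.7 and 10.3 disagree on what the extension will deliver.

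The p-value floors are also conditional. They assume one control and a two-sided test; one-sided, cohort C could reach 1/38 = 0.026.

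**Conclusion.** The point holds as a defect of the plan as written, and it can be repaired. On a same-visit reading the third-dose T cell comparison has one eligible control in the evaluable set, or none if that person declines, and no pairwise test can reach two-sided 0.05. A few non-evaluable controls could lower the floors without making the comparison informative. On the other reading the comparator is unstated and confounded with selection and dose number. Either way, no within-person analysis is specified and the pre-dose-3 PBMC sample is not assigned to the ELISpot. Neutralisation has no measurement at day 28 after dose 3 and none tied to the pre-dose draw, although 1.7 says it will be studied.

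The conclusion rests on the section 1.6 counts, full uptake for the figures at one control, and an assumed two-sided 0.05. It concerns secondary and exploratory endpoints only. It should be corrected but does not threaten the trial's main result.

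**What to change.** 1. In 10.2, make the third-dose T cell analysis a within-participant comparison of the pre-dose Vacc 3 sample with day 28 after Vacc 3. Report it per cohort, since section 3 expects the treatments to act differently, and give a pooled B–D estimate as a summary. Show cohort A after two doses as a descriptive reference only.
2. In 8.1.2 and 10.2, add Vacc 3 (pre-dose) to the T cell time points, using the PBMCs Table 2 already collects.
3. In 10.3, add Vacc 3 (pre-dose) and day 28 after Vacc 3 to the neutralisation time points, on blood already drawn for antibodies.
4. Keep the comparisons with cohort A at the other visits.

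The cost is a wording change plus extra ELISpot and neutralisation runs on at most about 63 participants' samples, with no new visits or draws. A before–after change has no concurrent control, so the report should say so. Cohort B, with at most 9 patients, will support only a descriptive result unless the change is large.

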#### 10.3 Other study parameters

- Dynamics of SARS-CoV-2 specific antibody concentrations will be analyzed, e.g. by calculating geometric mean fold-rise between baseline and post-baseline time points and antibody decay after day 28.
- In-depth flow-cytometric analyses for functional and phenotypical characterization of SARS-CoV-2 specific cellular responses will be performed by assigning proliferative capacity, cytokine production and phenotypical markers (>25 markers in parallel) in a subset of patients. These descriptive study parameters will not be statistically compared between cohorts.
- Baseline (immune) parameters will be related to vaccination response using univariate analysis.
- As a functional readout, the neutralizing capacity SARS-CoV-2 antibodies will be measured at baseline, 28 days and 6, 11 and 18 months after the second vaccination. Titers will be expressed as GMCs with 95% CIs for each cohort, for each time point.
- To assess induction of a mucosal antibody response, mucosal lining fluid samples will be collected for measurement of SARS-CoV-2-specific antibody concentrations with multiplex immunoassay at baseline and at 28 days after the second vaccination. Additional analyses e.g. neutralizing capacity of mucosal antibodies can be performed.
- Mucosal SARS-CoV-2-specific antibody response will be correlated with serum SARS-CoV-2-specific antibody response.

- Information on incidence of SARS-CoV-2 infection, outcome of COVID-19 during 18 months after the second vaccination will be collected. The number of participants tested, the number of SARS-CoV-2 tests and test results will be reported. For participants with a positive test, information about severity will be presented including hospital admissions, use of oxygen, intensive care admission and mechanical ventilation.
- Levels of SARS-CoV-2 S-specific IgG antibodies before the third vaccination, and at day 28 after the third vaccination will be measured to assess antibody response in participants with an inadequate response to two mRNA-1273 vaccinations.
- Safety of a third mRNA-1273 vaccination in participants with an inadequate response to two mRNA-1273 vaccinations as mentioned under 10.2.

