#### 1.4 COVID-19 vaccination in patients with cancer

Patients with cancer have an increased risk for an adverse outcome of COVID-19 [13-15]. As a consequence, many patients strictly adhere to self-isolation, resulting in loneliness and loss of quality of life. Therefore, vaccination needs to be prioritized for these vulnerable patients. In addition, effective COVID-19 vaccination is of extreme importance to protect patients with cancer to continue care and cure. An immune response to vaccination would not only protect them from life-threatening COVID-19 but also allow close contact with their loved ones. Therefore, patients and patient organizations have already claimed prioritization of vaccination against COVID-19 for patients with cancer.

For proper protection against COVID-19 by vaccination, specific immune responses need to be induced. SARS-CoV-2 specific immune cells are essential to combat the virus. B cells are important for antibody responses to neutralize the virus, while CD8 positive T cells can specifically recognize and eradicate virus-infected cells. In addition, CD4 positive T cells are required for providing necessary help to B cells and CD8 positive T cells. Cancer immunotherapy activates T cells against cancer cells by blocking the interaction between Programmed Death 1 (PD1) and its ligand (PD-L1) [33]. How this treatment impacts immune responses to vaccination is unknown. Chemotherapy causes bone marrow suppression and reduces the number of immune cells in the blood circulation, which may hamper the induction of protective immune responses after vaccination as suggested in studies on

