# 2. OBJECTIVES

Primary Objective:

 To assess the antibody based immune response after vaccination against COVID-19 in patients with cancer treated with immunotherapy and/or chemotherapy as compared to controls

Secondary Objectives:

- To assess adverse events (AEs) after vaccination against COVID-19 in patients with cancer treated with immunotherapy and/or chemotherapy
- To assess durability of the antibody response in patients with cancer treated with immunotherapy and/or chemotherapy
- To analyze the SARS-CoV-2 specific T cell response after vaccination in patients with cancer treated with immunotherapy and/or chemotherapy

Exploratory Objectives:

- To perform in-depth analysis of cellular immune responses in patients with cancer treated with immunotherapy and/or chemotherapy
- To identify baseline (immune) parameters associated with vaccination response in patients with cancer treated with immunotherapy and/or chemotherapy
- To assess the neutralizing capacity of antibodies against SARS-CoV-2 after vaccination in patients with cancer treated with immunotherapy and/or chemotherapy
- To analyze induction of mucosal antibodies against SARS-CoV-2 in mucosal lining fluid samples. To describe the incidence of SARS-CoV-2 infection, outcome of COVID-19 during 12 months after vaccination in patients with cancer treated with immunotherapy and/or chemotherapy
- To analyze SARS-CoV-2-binding antibody concentration after a third vaccination in participants without an adequate antibody response after two vaccinations
- To analyze safety of a third vaccination

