#### 10.1 Primary study parameter

The primary study parameter is the antibody based immune response to vaccination against COVID-19 on day 28 after the second vaccination in cancer patients as compared to individuals without cancer. SARS-CoV-2 S-specific serum IgG antibody concentrations will be measured at the RIVM using a validated fluorescent bead-based multiplex-immunoassay [40]. Geometric mean concentrations (GMCs) and 95% confidence intervals (CIs) will be calculated for the SARS-CoV-2 S-protein-specific IgG antibodies at baseline and day 28 after vaccination for each cohort. Participants will be classified as responders or non-responders. The definition of response is seroconversion defined as presence of SARS-CoV-2 spike S1-specific IgG antibodies with a threshold for seropositivity based on Receiver Operator Curve (ROC) analysis and set at 1.04 AU/mL [41]; in individuals without measurable anti-S antibodies at baseline. Concentrations have been interpolated from a reference consisting of pooled sera using a 5-parameter logistic

fit that was calibrated against the NIBSC/WHO COVID-19 reference serum 20/136 and expressed as international binding antibody units per ml (BAU/mL). The value of 1.04 AU/mL corresponds to 10 BAU/mL. Participants who are seropositive at baseline will not be included in the analysis of the primary endpoint. The percentage of responders and corresponding 95% CI for each cohort will be calculated. The percentage of responders of each patient cohort will be compared with the percentage responders in the group without cancer, using a modified standard fixed-delta test [42].

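### Section 10.3 relates baseline parameters to an unspecified vaccination response by univariate analysis only: with seroconversion as outcome there are about 7 patient non-responders, and pooling patient cohorts would mix marker and cohort effects

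*Combined protocol and SAP*

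**What the plan says.** Section 2 lists as an exploratory objective: "To identify baseline (immune) parameters associated with vaccination response in patients with cancer treated with immunotherapy and/or chemotherapy". The objective therefore concerns cohorts B, C and D, not the controls. The whole analysis plan for it is one sentence in section 10.3: "Baseline (immune) parameters will be related to vaccination response using univariate analysis". That sentence names no outcome scale, no analysis population and no handling of cohort.

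The documents offer three candidate antibody outcomes:

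- **Seroconversion.** Section 10.1: "The definition of response is seroconversion defined as presence of SARS-CoV-2 spike S1-specific IgG antibodies with a threshold for seropositivity", set at 10 BAU/mL. Section 8.1.1 defines response in the same way, without the number.
- **Adequate response.** Section 1.6 introduces a 300 BAU/mL cutoff, and the footnotes to Tables 1 and 2 use it to select participants for the third vaccination.
- **IgG level.** Section 10.2 compares day-28 S-specific IgG concentrations between cohorts.

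Section 1.6 already reports the day-28 results. A response above 10 BAU/mL "was found in 100%, 99.3%, 97.4%, and 100% of the participants in cohorts A, B, C, and D, respectively". At 300 BAU/mL, "99.6% (A), 93.1% (B), 83.8% (C), and 88.8% (D) had an adequate response".

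**The concern.** Two gaps in one sentence matter together.

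First, the outcome. In the methods and analysis sections, the only formal definition of a responder is seroconversion, so that is the natural reading of vaccination response. The sample size section worked with scenarios of 60% and 40% response under chemotherapy, which would have left many non-responders to study. The results in section 1.6 left very few, and the sentence in 10.3 does not take this into account.

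Second, the cohorts. Response differs by cohort, and baseline immune markers are likely to differ by cohort as well. Section 1.4 says: "Chemotherapy causes bone marrow suppression and reduces the number of immune cells in the blood circulation". If patients are pooled and each marker is tested alone, a marker of treatment type can pass for a predictor of response.

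At stake is the reliability of one exploratory result. Real predictors could be missed, treatment markers could be reported as immune predictors, and the outcome could be picked from three candidates after the day-28 results are known.

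**Working it through.** **Inputs.** From section 1.6, the evaluable participants are "240 individuals without cancer and 131 patients receiving immunotherapy, 229 patients receiving chemotherapy, and 143 patients receiving chemo-immunotherapy". These sum to 240 + 131 + 229 + 143 = 743, the total given there, and the patients to 131 + 229 + 143 = 503. Response rates are those quoted above. The documents give no power or event count for this analysis, so two-sided 5% and 80% power are assumed: z = 1.960 + 0.842 = 2.802.

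**Planned non-responders.** The plan's own sample sizes reproduce with n = (1.645 + 0.842)² × [p₁(1−p₁) + p₂(1−p₂)] / (margin − difference)²:

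- 90% vs 90%, margin 10%: 112 per group.
- 90% vs 60%, margin 40%: 205 per group.

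Scenario 1 at those numbers implies 112 × 0.10 + 2 × 205 × 0.40 = 11.2 + 164 ≈ 175 patient non-responders.

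**Observed events**, cohort size × (1 − response rate):

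| Cohort | n | at or below 10 BAU/mL | below adequate (300 BAU/mL) |
|---|---|---|---|
| B | 131 | 0.92, so 1 | 9.04, so 9 |
| C | 229 | 5.95, so 6 | 37.10, so 37 |
| D | 143 | 0 | 16.02, so 16 |
| Patients | 503 | 7 | 62 |

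For cohort B, 130/131 is 99.2% rather than the printed 99.3%, but 1 is the only integer close to it.

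**Detectable marker difference**, 2.802 × √(1/n₁ + 1/n₂):

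- Seroconversion, 7 vs 496: 1.07 SD. Within cohort C alone, 6 vs 223: 1.16 SD. B has one event and D none.
- 300 BAU/mL, 62 vs 441: 0.38 SD. By cohort: B (9 vs 122) 0.97, C (37 vs 192) 0.50, D (16 vs 127) 0.74 SD.

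For a binary marker present in 50% of responders (assumed), exact Fisher power with 7 events is about 6% at an odds ratio of 2, 14% at 3, 28% at 5 and 52% at 10. With 62 events, approximate power is about 70% at 2 and 97% at 3.

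**Continuous IgG.** Detectable correlation is tanh(2.802/√(N−3)). For N = 503 it is 0.12. By cohort it is 0.24 (B), 0.18 (C) and 0.23 (D).

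**Confounding if patients are pooled.** Take a marker unrelated to response within cohorts but shifted by d SD in cohort C only. The expected spurious difference is d × (share of C among non-responders − share of C among responders).

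- 10 BAU/mL: 6/7 − 223/496 = 0.857 − 0.450 = 0.408. For d = 0.5 to 1, this is 0.20 to 0.41 SD.
- 300 BAU/mL: 37/62 − 192/441 = 0.597 − 0.435 = 0.161. For d = 0.5 to 1, this is 0.08 to 0.16 SD.

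Cohort D also receives chemotherapy. If the shift is equal in C and D, the figures are d × (6/7 − 366/496) = 0.119d, or 0.06 to 0.12 SD, and d × (53/62 − 319/441) = 0.131d, or 0.07 to 0.13 SD.

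Against the standard error of the comparison, the largest shifts are 0.41/0.381 ≈ 1.1 standard errors at 10 BAU/mL and 0.16/0.136 ≈ 1.2 at 300 BAU/mL. Moving to the higher cutoff restores power but does not remove the confounding.

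**The case against.** A reader might infer that the objective cannot be met because there are only 7 non-responders. The documents do not support that. Section 10.3 does not tie vaccination response to seroconversion. The 300 BAU/mL cutoff is defined in 1.6, is used in 1.7 to count suboptimal and non-responders, and is operative in Tables 1 and 2. It gives about 62 patient events, with some in every patient cohort. IgG levels are measured as well. Seven events is the outcome of one reading.

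A reader might also infer that the plan pools the cohorts. It does not say so, and most comparisons in 10.1 and 10.2 are made cohort by cohort. A by-cohort univariate analysis would avoid the confounding. Confounding is therefore a risk left open, not a stated feature.

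The objective is also exploratory, without a hypothesis test or decision rule, and univariate description is a common choice there. The Summary's remarks on whom to vaccinate or protect by other means concern the study as a whole. The 60% and 40% rates were scenarios for a rate the protocol calls unknown.

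All of this stands, and it limits the point to under-specification plus a method weaker than the data allow. It does not remove the point. Informative outcomes exist, but none is assigned to this objective. The by-cohort route fails for seroconversion and is thin for B and D at 300 BAU/mL. The pooled route is confounded under either cutoff.

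**Conclusion.** The point holds as a gap in specification with a measurable consequence. If response means seroconversion, the analysis can detect only very large associations (about 1.07 SD, 7 vs 496) and cannot be done by cohort or sensibly adjusted. If it means adequate response, power is usable (about 0.38 SD, 62 vs 441), but an unadjusted pooled analysis can still show a spurious difference of up to about 0.16 SD for a marker shifted by 1 SD in cohort C.

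These figures rest on event counts rounded from the percentages in 1.6, on 80% power and two-sided 5%, and on illustrative marker shifts of 0.5 to 1 SD, which the documents do not give. They also assume that the marker is measured in every evaluable patient. Flow cytometry is planned only in a subset, so precision there is lower by an amount that the documents do not allow one to state. The primary analysis is not affected.

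**What to change.** In section 10.3, state that:

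- in cohorts B to D, each baseline parameter is related to log-transformed day-28 S-specific IgG by linear regression that includes cohort and age (section 3 itself names age as an important predictor of vaccine response), with per-cohort estimates shown;
- adequate response at 300 BAU/mL, adjusted for cohort, is a supporting analysis;
- the univariate results are kept as description;
- the outcome scale was chosen after the first day-28 results were known;
- the number of patients with each marker measured is reported, because the detectable correlation of about 0.12 applies only where all 503 have a value.

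The cost is a change of wording and a regression on data already planned or held, with no new visits or samples. The downside is that effects are read as fold-changes in IgG rather than as odds of response, and that the choice is post hoc, which is acceptable for an exploratory objective if declared.
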